7.3.4. Exploratory Hypotheses:	25
7.4. ADDITIONAL STATISTICAL CONSIDERATIONS	26
7.4.1. Handling of Missing Data	26
7.4.2. Multiplicity	26
7.4.3. Interim Analysis	26
7.4.4. Analysis Sets	26
7.4.5. Pre-specified analysis	26
7.5. DEFINITIONS	26
7.6. RECORDING/REPORTING OF ADVERSE EVENTS	27
7.7. STOPPING RULES.....	28
7.8. MEDICAL MONITORING	28
8. DATA HANDLING AND RECORD KEEPING.....	28
8.1. CONFIDENTIALITY	28
8.2. SOURCE DOCUMENTS	28
8.3. CASE REPORT FORMS	29
8.4. RECORDS RETENTION	30
9. STUDY MONITORING, AUDITING, AND INSPECTING	30
9.1. STUDY SITE MONITORING PLAN	30
10. ETHICAL CONSIDERATIONS.....	31
10.1. CONFLICT OF INTEREST.....	31
11. REFERENCES.....	31

Study Summary

Title	Screening for Peripartum Cardiomyopathies using Artificial Intelligence (SPEC-AI) – Nigeria
Running Title	Screening for cardiac dysfunction in pregnancy
Protocol Number	22-000539
Phase	Other
Methodology	Prospective randomized controlled trial
Overall Study Duration	12 months
Subject Participation Duration	Participation will range from a single encounter/visit to a maximum of 12 months
Single or Multi-Site	Multi-Site
Objectives	To determine the effectiveness of an AI-enabled ECG to detect cardiomyopathy and its impact on clinical outcomes in a predominantly Black obstetric population in Nigeria
Number of Subjects	1,400 enrolled / 1,200 accrued
Diagnosis and Main Inclusion Criteria	
The condition being studied is pregnancy related cardiomyopathy
 
Inclusion Criteria:
 
 • Adult female age of 18 – 49 years • Currently pregnant or within 12 months postpartum • Able to provide consent
Study Product, Dose, Route, Regimen	
Intervention: AI algorithm to evaluate electrocardiogram data and generate prediction probabilities for a diagnosis of cardiomyopathy. To be performed intermittently at pre-specified time points during the study
 
Drug, Dose, Route: Not applicable

Statistical Methodology	The analysis plan will focus on comparing AI-ECG algorithm predictions of low ventricular ejection fraction (<50%) with baseline echocardiograms as the reference criterion (clinical standard) and evaluating the impact of AI-ECG screening on maternal outcomes.

1. Introduction

This document is a protocol for a human research study. This study will be carried out in accordance with the applicable United States government regulations, Mayo Clinic research policies and procedures and local regulations in Nigeria as applicable including data privacy rules and ethics board requirements

1.1. Background

An artificial intelligence (AI) model was developed by members of our Mayo Clinic team to identify cardiac dysfunction (defined as left ventricular ejection fraction (LVEF) $\leq 35\%$) using an electrocardiogram (ECG) alone with high discrimination - area under the curve (AUC) of 0.93. (Z. I. Attia et al., 2019) We validated this AI-ECG model in the emergency room setting among patients with undifferentiated dyspnea (D. Adedinsewo et al., 2020) and in a clinical trial among patients seen in the primary care setting and it remained robust. (Yao et al., 2021)

Given that cardiovascular disease (CVD) is the leading cause of pregnancy-related mortality, we retrospectively evaluated the AI-ECG among pregnant and postpartum women seen across the Mayo Clinic enterprise and found it to be effective with an AUC of 0.92 (D. A. Adedinsewo et al., 2021). These prior studies provide preliminary data and support the feasibility of using the AI-ECG in a clinical setting. It also establishes the premise for its application to routine obstetric and postpartum care. Black women are disproportionately affected by pregnancy-related cardiac dysfunction (cardiomyopathy) and underrepresented in clinical research studies. To reduce health disparities and promote health equity, a prospective evaluation of the AI-ECG in a Black obstetric population is essential.

Although maternal mortality has been on the decline worldwide, maternal mortality rates in the U.S. have increased over the last 20 years with rates 3 times higher now than in the 1980s. (CDC:Division of Reproductive Health; G.B.D. Maternal Mortality Collaborators, 2016) . Cardiomyopathy (a disease of the heart muscle that makes it difficult to pump blood to the rest of the body) is responsible for the majority of deaths among pregnant and postpartum women, with Black women bearing a disproportionate burden of disease. (Melinda B Davis et al., 2021; Mehta et al., 2020) Failure to identify CVD symptoms is believed to be contributing to this critical health inequity. (ACOG, 2019) In low-income countries, particularly sub-Saharan Africa, maternal mortality rates are up to 40 times higher (1074/100,000 live births) than in the U.S. (G.B.D. Maternal Mortality Collaborators, 2016). This issue is of global concern which made it a key priority item on the United Nations Millennium development goals. (Hogan et al., 2010) What remains unknown are effective methods to screen for cardiomyopathy during pregnancy and the postpartum period. Symptoms of normal pregnancy and cardiomyopathy frequently overlap (Hameed et al., 2015) making it difficult for clinicians to identify high-risk women in routine obstetric practice. Thus, there is a *critical need* to identify simple and effective screening tools to detect cardiomyopathy in pregnant and postpartum women. In the absence of this knowledge, the development of effective intervention strategies to decrease cardiomyopathy-related maternal mortality among Black women will remain challenging.

Our *long-term goal* is to identify effective strategies for cardiomyopathy detection among pregnant and postpartum women so that appropriate interventions can be developed to decrease cardiomyopathy-related maternal mortality. The *overall objective of this proposal* is to determine if an AI-ECG is an effective tool to screen for cardiomyopathy among pregnant and postpartum women. Our *central hypothesis* is that an AI-ECG improves the diagnosis of cardiomyopathy among pregnant and postpartum women. We have based our central hypothesis upon data from a retrospective analysis we conducted among pregnant and postpartum women seen across the Mayo Clinic enterprise which showed the AI-ECG was effective for cardiomyopathy detection. (D. A. Adedinsewo et al., 2021) Our *rationale* for this project is that its successful completion would provide a cost-effective and scalable option for cardiomyopathy screening in the obstetric population and enable the development of appropriate interventions targeted at reducing cardiomyopathy-related mortality. We are *well-positioned to lead this project* based on our team's expertise and experience with developing and validating AI-ECG models for CVD detection. Members of our team were the first to develop and publish results supporting the AI-ECG as an effective method to screen for cardiomyopathy. (Z. I. Attia et al., 2019)

Following the successful completion of this project, we expect to have established the effectiveness of a novel AI-ECG to detect cardiomyopathy in Black pregnant and postpartum women that will ultimately improve diagnosis and decrease maternal mortality. This achievement would not only cause a positive paradigm shift in the field of obstetric care, but it would also help (1) promote health equity, (2) increase the inclusion of women in cardiovascular clinical research, and (3) support the use of AI tools to improve cardiovascular care.

1.2. Investigational Agents

This protocol intends to evaluate a standard clinical 12-lead ECG recordings (Fig 1) and portable ECG device recordings (Fig 2 and 3) analyzed with AI-ECG algorithms for cardiomyopathy detection. These algorithms are investigational at this time and not yet approved for medical use by the US Food and Drug Agency.

[figure not shown]

Figure 1. Standard 12-lead ECG

Figure 2. AliveCor 6L wireless ECG device with portable 6-lead ECG displayed

[figure not shown]

Figure 3. Eko DUO Digital Stethoscope with portable single-lead ECG displayed

1.3. Preliminary Data

An artificial intelligence (AI) model has been developed by members of our Mayo Clinic team to identify cardiac dysfunction (originally defined as left ventricular ejection fraction (LVEF) $\leq 35\%$; although alternative LVEF thresholds are under investigation including $\leq 40\%$ in the current registration trial for the LVEF algorithm) using an electrocardiogram (ECG) alone with high discrimination - area under the curve (AUC) of 0.93. (Z. I. Attia et al., 2019). The initial model was developed using a dataset of 97,829 patients (with paired ECG and echocardiograms).

The ROC curve from the published manuscript is shown below.

[figure not shown]

Figure 4. Network ROC and sensitivity and specificity across age and gender subsets.

An ongoing pilot study has collected prospective ECG and echocardiogram data under Mayo Clinic IRB 21-003427 and we have enrolled 66 out of a target 100 study participants including standard 12-lead and portable ECG device recordings obtained at pre-specified intervals during the study.

1.4. Risks and Benefits

The risks of this research study are expected to be minimal and represent the general risks associated with prenatal wellness screening and routine medical care. However, there are some risks that are associated with study procedures. Anticipated study related risk includes the potential skin irritation from placement of ECG lead electrode stickers directly on the skin for 12-lead ECG recordings. To minimize risk for skin irritation, the ECG lead electrode stickers will only be placed on the skin for the duration that the ECG is recorded as with standard clinical practice with an estimated duration of contact less than 5 mins.

Another risk in this study is the communication of results for the attention control arm. Two experimental algorithms will be used that predict biological sex and age. There is a potential for discordance in sex to be reported along with large variances in estimated age. The implications of such predictions is not yet known. Study staff will be trained on the algorithms and a study information sheet will be used to describe the study procedures and test results.

As with all research, there is a chance that confidentiality could be compromised; however, we take precautions to minimize this risk.

- All enrolling sites in Nigeria will maintain their own confidential screening logs following local institutional procedures, local regulations and ethics boards requirements.

- Confidentiality of patient information will be maintained by assigning study identifiers to the medical data.
- Digital ECG data will be sent using a secure, encrypted online-based file share service with detailed instructions provided to study sites and as detailed in the study's Manual of Operations. No identifiable data received will be shared external to Mayo Clinic. Only study staff will have access to the data collected.
- Additional Considerations: The following is a list of study participant confidentiality safeguards:
 - **Data flow procedures** – Data identifying participants should not be transmitted from study sites to the Coordinating Center.
 - **Electronic files** – Data identifying participants that are stored electronically should be maintained in an encrypted form or in a separate file with device password protection.
 - **Forms** – Forms or pages containing personal identifying information should be separated from other pages of the data forms and retained in a secure location.
 - **Data listings** – Participant name, name code, hospital chart, record number, Social Security Number, or other unique identifiers should not be included in any published data listing.
 - **Data distribution** – Data listings that contain participant name, name code, or other identifiers easily associated with a specific participant should not be distributed.
 - **Data disposal** – Computer listings that contain participant-identifying information should be disposed of in an appropriate manner.
 - **Access** – Participant records should not be accessible to persons outside the study without the express written consent of the participant.
 - **Storage** – Study forms and related documents retained both during and after study completion should be stored in a secure location.
 - **Passwords** – Passwords provide limitations on general access to computer systems and to the functions that individuals can use. Passwords should be changed on a regular basis.
 - **User Training** – Study staff with access to clinical computer systems should be trained in their use and in related security measures. Training should include explanations of how to access the system and a discussion of the need for, and importance of, system security.

There may be direct benefit to study subjects participating in this research study as early heart failure or other heart condition may be detected sooner than it may have been otherwise. Other than that, study participants may not receive any other direct benefit from participating in this study. The results of this study could potentially lead to a positive paradigm shift in the field of obstetric care, and help (1) promote health equity, (2) increase the inclusion of women in cardiovascular clinical research, and (3) support the use of AI tools to improve cardiovascular care.

2. Study Objectives

2.1. Primary Objective

The overall objective of this study is to determine if an artificial intelligence enhanced electrocardiogram (AI-ECG) is an effective tool to screen for cardiomyopathy (LVEF < 50%) in a predominantly Black population of pregnant and postpartum women.

2.2. Secondary Objectives

- a) Determine if an AI-ECG improves the detection of cardiomyopathy among Black pregnant and postpartum women.
- b) Determine the effectiveness pf an AI-ECG for cardiomyopathy detection at different LVEF cut offs (<45%, <40%, \leq 35%)

2.3. Exploratory Objectives

- (a) Determine the diagnostic yield of an AI-ECG on cardiovascular outcomes among pregnant and postpartum women.
- (b) Determine the impact of an AI-ECG on echocardiography utilization
- (c) Develop and evaluate the diagnostic performance of an AI-enhanced point of care screening tool using portable, smartphone-compatible ECG devices (AIPOC-ECG) for the detection of cardiomyopathies in pregnant and postpartum women.

[figure not shown]
3. Study Design

3.1. General Description

Nigeria is estimated to have the highest incidence of peripartum cardiomyopathy in the world, as high as 1 in 100 deliveries (M. B. Davis, Arany, McNamara, Goland, & Elkayam, 2020). As such, a prospective randomized-controlled study will be conducted at multiple sites in Northern and Southern Nigeria with study participants randomly assigned in a 1:1 fashion to the intervention vs. the control arm over a 12 to 18-month period.

Following informed consent, all participants will have ECGs acquired at baseline and at selected intervals during pregnancy and postpartum (Fig 5 and 6). Half of the participants will be randomized to either undergo:

- AI-ECG screening for cardiomyopathy + baseline echocardiography + AI-ECG age and sex estimation (intervention arm) or
- Standard of care + AI-ECG age and sex estimation only (Zachi I Attia, Paul A Friedman, et al., 2019) (attention control arm).

**Figure 5. Patient enrollment flow diagram**

[figure not shown]

Figure 6. Study procedures

All patients will have follow-up and medical record review to ascertain the development of study clinical outcomes. Patients can enter the study at any time point (Fig 6) during pregnancy or the postpartum period (up to 12 months after delivery). All women will have a standard 12-lead ECG performed at the time of enrollment and at pre-specified intervals through 12 months postpartum or study end (whichever is earlier). ECGs will be performed up to 7 times during the study period including during each trimester of pregnancy (up to 3 ECGs), post-delivery ECGs may be taken between delivery and 6 weeks (1 ECG), between 6 weeks and 3 months (1 ECG), between 3 and 5 months (1 ECG), and between 5 and 12 months postpartum (1 ECG). Only participants in the intervention arm will have a baseline echocardiogram as well as simultaneous portable ECGs recorded with near real-time provision of AI-ECG cardiomyopathy prediction. Additionally, a newly positive AI-ECG screen for cardiomyopathy during any of the 6 visits will trigger an echocardiogram for participants in the intervention arm. This strategy for performing echocardiograms was selected as it is not practical to obtain an echocardiogram during each prenatal care visit due to time, skilled expertise required, and cost. In addition, the negative predictive value of the AI-enabled ECG is known to be very high (consistently exceeding 95%) in multiple internal and external patient populations (D. Adedinsewo et al., 2020; Attia et al., 2021; Z. I. Attia et al., 2019). Patients in the intervention group with cardiomyopathy detected on an echocardiogram will have a repeat echocardiogram performed at the end of the study period (or at 12 months postpartum depending on which is earlier) as part of the study protocol to assess for left ventricular recovery (Fig 6).

All echocardiograms will be reviewed by the local cardiologists and performed in accordance with American Society of Echocardiography guidelines for ejection fraction assessment as part of the study. LVEF measurements will be recorded for study participants using REDCap.

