6.3. Positive AI-ECG Screen/New Cardiomyopathy Diagnosis (Intervention arm only)

In the event that the AI-ECG detects cardiomyopathy (and baseline echocardiogram showed normal ejection fraction), this would trigger an echocardiogram as part of the research study protocol and the results would be reviewed by a local cardiologist and provided to the managing obstetrician which have already been identified at each site. For participants with newly diagnosed cardiomyopathy (confirmed by echocardiography), the decision to initiate guideline directed medical therapy or other treatment will be based on a clinical evaluation by a local cardiologist at each site, local clinical practice standards, treatment options available and patient preferences.

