7.1. Sample Size Determination

LVEF<50% is not expected to be diagnosed in the control arm due to the lack of routine echocardiograms, but for sample size calculations, we have assumed that 1% will be diagnosed based on literature derived incidence rate of 1 in 100 deliveries (M. B. Davis et al., 2020). With the AI-ECG screening, we hypothesize that an increase in the number of cases will be detected. For sample size estimation consideration, an unpublished, ongoing pilot study conducted in the US estimates the prevalence as 5.3% (3/57) for <=35% and 7% (4/57) for <50%. Sample size estimation is based on a conservative estimate of 4% in the AI-ECG arm. At the alpha=0.05 and 80% power, the sample size is estimated to be 424/group. For the secondary composite endpoint, approximately 5% of the sample is expected to experience hypertensive disorders (Ying, Catov, & Ouyang, 2018). We hypothesize that the addition of AI-ECG will increase the detection of cardiomyopathies and other structural defects of the heart. Accordingly, we assume composite event rates of 5% vs. 10% for the control vs. AI-ECG arm. At 80% power and alpha=0.05, a sample size of 434/group is required. For the final sample size, these estimates are rounded up to 500/group (1000 total) to account for the uncertainties in the calculations. Due to the variability in the occurrence of cardiomyopathy across sites, need to account for study participant withdrawal from the study, no-shows to study visits, and loss to follow up, we plan to enroll 1,400 patients to achieve an accrual target of 1,200 participants while ensuring balanced accrual across all 6 sites.

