7.3. Statistical Hypotheses and planned analyses

7.3.1. Descriptive Statistics

Descriptive statistics including measures of central tendency for numeric variables and frequency distributions for categorical variables will be calculated, as appropriate for all variables. Demographic, clinical, and outcome variables (primary and secondary) will be tabulated for all enrolled study participants. These data will be summarized for the entire cohort and stratified by randomized group and region. We will summarize the measures of diagnostic performance (i.e., AUC, sensitivity, specificity) stratified by study entry to account for the differential follow-up testing that may have occurred as a result of the AI-ECG screening

7.3.2. Primary Hypothesis:

AI-ECG is an effective tool to screen for cardiomyopathy, defined as LVEF < 50%, in pregnant women.

Statistical Hypothesis:

- $H_0: P_{\text{ai-ecg}} = P_{\text{control}}$
- $H_A: P_{\text{ai-ecg}} \neq P_{\text{control}}$

Where P defines the proportion of participants that have documented LVEF <50% by the conclusion of the study.

Primary analysis: A chi-square test without continuity correction will be applied to the resulting two by two table (rows: random treatment assignment, columns LVEF < 50% reported by conclusion of the study). The primary analysis will be conducted at the alpha=0.05 level of significance (two-sided).

7.3.3. Secondary Hypotheses:

AI-ECG will provide consistent performance across race, ethnicity, and postpartum enrollment status.

Secondary analysis: The introduction of stratification factors of race, ethnicity and postpartum status (all unique tables) will be used to produce a stratified contingency table. The Breslow-Day test of homogeneity of the odds ratio will be used to test for effect modification (differential treatment effects by strata). There is the potential for sparse strata with this analysis. If the odds ratio is not estimatable due to zero cells, the empirical logit estimator as well as pooled strata (to increase sample size for each strata) will be utilized.

An AI-ECG is an effective tool to screen for cardiomyopathy at different LVEF cut-off values (<45%, <40%, ≤ 35%).

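### AI-negative results after baseline are never checked by protocol echocardiography, so accuracy should be estimated from the baseline pairs only and each intervention-arm case labelled by how it was found

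*Combined protocol and SAP*

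**What the plan says.** Every woman in the intervention arm is to have a baseline echocardiogram paired with a 12-lead ECG (sections 3.1 and 6.1.2). After that, protocol echocardiography depends on the AI result. Section 6.3 states: "In the event that the AI-ECG detects cardiomyopathy (and baseline echocardiogram showed normal ejection fraction), this would trigger an echocardiogram". The end-of-participation echocardiogram is reserved for women whose cardiomyopathy has already been found. No section plans one for a woman whose follow-up AI-ECGs stay negative.

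Sections 3.1 and 6.2 give two reasons. The main one is that "it is not practical to obtain an echocardiogram during each prenatal care visit due to time, skilled expertise required, and cost". The additional one is that "the negative predictive value of the AI-enabled ECG is known to be very high (consistently exceeding 95"%) in other populations.

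Three parts of the plan bear on how accuracy is analysed:

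- The Study Summary names baseline echocardiograms as the reference standard.
- Section 7.3.3 evaluates the algorithm in the intervention arm, where echocardiograms are done under the protocol. It does not say baseline only.
- Section 7.3.1 lists AUC, sensitivity and specificity, and stratifies them by study entry to deal with follow-up testing that the AI result itself may have caused.

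The primary analysis (section 7.3.2) compares, by randomised arm, the proportion with LVEF <50% documented by the end of the study, however it came to be documented.

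**The concern.** A screening test is judged by the cases it misses as well as those it finds. During follow-up this design checks positives and leaves negatives unchecked, which is partial verification. If triggered echocardiograms enter the accuracy analysis, every one of them sits in the AI-positive row. They can add true and false positives but never a missed case, so sensitivity is pushed up and specificity down. Stratifying by study entry does not help, because within each stratum the AI-negative follow-up results still have no reference result.

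The NPV statement could reassure a reader that misses are rare. NPV depends heavily on prevalence, and at low prevalence it is high even for a poor test.

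Separately, the primary proportion does not distinguish a case that AI-ECG flagged from one found by the baseline echocardiogram with a negative ECG, or by a clinician. The arm comparison alone therefore does not show how many cases AI-ECG found.

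**Working it through.** **Inputs.** Section 7.1 gives the control rate ("we have assumed that 1% will be diagnosed based on literature derived incidence rate of 1 in 100 deliveries") and the intervention rate ("Sample size estimation is based on a conservative estimate of 4% in the AI-ECG arm"). It also reports a US pilot that "estimates the prevalence as 5.3% (3/57) for <=35% and 7% (4/57) for <50"%. Accrual of 1,200 at 1:1 gives about 600 women in the intervention arm. The prevalence, sensitivity and specificity behind the quoted NPV are not given, so that figure itself cannot be reproduced.

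**1. Are 1% and 4% the sizing rates?** Two-sided chi-square without continuity correction, alpha 0.05, power 80%:

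n = [1.960·√(2·0.025·0.975) + 0.842·√(0.01·0.99 + 0.04·0.96)]² / 0.03² = (0.4327 + 0.1850)² / 0.0009 ≈ 424.

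This matches the plan ("At the alpha=0.05 and 80% power, the sample size is estimated to be 424/group").

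**2. What NPV does a useless test reach?** If the result is unrelated to disease, NPV = 1 − prevalence. More generally, NPV = sp(1−p) / [sp(1−p) + (1−se)p]. Specificity of 90% is assumed in the last three columns.

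| Prevalence | Unrelated to disease | se 0% | se 50% | se 90% |
|---|---|---|---|---|
| 1% | 99.0% | 98.9% | 99.4% | 99.9% |
| 4% | 96.0% | 95.6% | 97.7% | 99.5% |
| 5.3% (3/57) | 94.7% | 94.2% | 97.0% | 99.4% |
| 7.0% (4/57) | 93.0% | 92.3% | 96.0% | 99.2% |

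The break-even prevalence is 5%. Below it, an NPV above 95% does not separate AI-ECG from chance. At the pilot rates a useless test falls just short, but a test that misses half the cases still passes. The pilot rates rest on 3 and 4 women of 57 (exact 95% intervals 1.1–14.6% and 1.9–17.0%). They are prevalences, whereas follow-up concerns new onset after a normal baseline, for which 1 in 100 is the nearest documented rate.

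**3. Can follow-up reveal misses?** Assume 600 women and new-onset risk between 1% and 4%, giving 6 to 24 new cases. At 50% sensitivity 3 to 12 are missed; at 90%, 0.6 to 2.4. Protocol echocardiograms show only the triggered cases. Three triggered cases could mean 6 new cases at 50% sensitivity (6/600 = 1%), or 3/0.9 = 3.3 new cases at 90% (3.3/600 = 0.56%). The data cannot tell these apart.

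**4. What would pooling do?** Assume 600 women, 3% affected at baseline (18) and 1% new during follow-up (6), with sensitivity constant and no clinically found cases entered:

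- True sensitivity 50%: baseline pairs give 9/18 = 50%; pooled, (9+3)/(18+3) = 12/21 = 57.1%.
- True sensitivity 90%: baseline pairs give 16.2/18 = 90%; pooled, (16.2+5.4)/(18+5.4) = 21.6/23.4 = 92.3%.

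Triggered echocardiograms taken alone give 100% sensitivity and 0% specificity whatever the truth, because only positives are verified.

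**The case against.** The strongest case against is that the plan already does most of what is needed. Practicality, not NPV, leads the rationale, and removing the NPV sentence would leave the design unchanged. The Study Summary names the baseline echocardiogram as reference, section 7.1 does not rely on NPV, and section 7.3.3 promises STARD reporting with confidence intervals and fractions, so a sensitivity fraction would show the number missed. Section 7.3.1 shows that the authors noticed the differential testing. New-onset cases will be few, and women with a single visit (section 3.3) contribute no follow-up at all.

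Much of this stands. It limits the point to an analysis specification that is incomplete and partly inconsistent. It does not close the gap: section 7.3.3 omits the baseline restriction, and stratifying by study entry cannot supply reference results that were never obtained.

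Several stronger readings are tempting, and the documents do not support them:

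- *NPV is the sole justification for the echocardiography strategy.* It is the second of two reasons.
- *A useless test exceeds 95% at every rate in the plan.* This is true at 1% and 4%, but not at the pilot's 5.3% and 7%.
- *The trial will report a flattering NPV.* The named measures are AUC, sensitivity and specificity.
- *Clinician-found cases bias the primary test towards AI-ECG.* They count in both arms. Dropping them from one arm would itself create bias.
- *The trial cannot measure misses at all.* Baseline pairs can, since the whole arm is to be verified, and symptomatic later misses may surface as new clinical diagnoses at Visits 2–7 or in record review.

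**Conclusion.** The point holds in a limited form. AI-negative follow-up results have no protocol verification, so follow-up sensitivity, specificity and NPV cannot be estimated without bias. The quoted NPV does not fill that gap: at the sizing rates a useless test reaches 99% and 96%. The plan leaves open whether triggered echocardiograms enter the accuracy estimates. If they do, sensitivity is inflated, by about 7 percentage points at a true 50% and 2 points at a true 90% in the illustration above. Those sizes rest on the assumed 3% and 1% case split, 600 women and constant sensitivity; the direction of the bias does not depend on the split.

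Baseline accuracy is unaffected provided the baseline echocardiograms are done as planned. The primary comparison by randomised arm is not invalidated and the sample size is unaffected. What is at stake is how far the results can be read as evidence about AI-ECG itself, especially for repeated screening.

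**What to change.** 1. In sections 7.3.1 and 7.3.3, state that AUC, sensitivity and specificity are estimated only from the paired baseline ECG and baseline echocardiogram, in line with the Study Summary. Give the number of LVEF <50% cases that AI-ECG missed. Do not present stratification by study entry as a correction for follow-up testing.
2. Report follow-up separately, as the yield and positive predictive value of AI-triggered echocardiograms. Add interval cases, defined as LVEF <50% found clinically after a normal baseline echocardiogram with the preceding AI-ECG negative. State that these are a lower bound on misses.
3. Leave the primary test in section 7.3.2 as it is. Beside it, tabulate each intervention-arm case by detection route: baseline echocardiogram with AI-positive ECG, baseline echocardiogram with AI-negative ECG, AI-triggered, or clinical.

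The cost is SAP wording and one classification variable, built from AI-ECG results, echocardiogram reports and new clinical diagnoses already due to be collected. No echocardiograms are added. The downside is a narrower claim: the trial could report what serial AI-ECG found and the misses that came to light clinically, but not its sensitivity for new-onset disease.
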